#### IBM SPSS Sample Power Output – Screenshot

Estimated overall drop-out rate is 56% which leads to the requirement of enrolling an additional 6 subjects into the clinical investigation.

Sample Size	Overall number of subjects to be enrolled: 16 subjects (rounded up to 20 subjects)
Overall Sample Size (multiplied by number of indications = 5)	100 subjects

Table 2b: Sample Size Justification (RSA)

In conclusion, the calculated number of subjects to be enrolled (10) plus the estimated overall drop-out rate of 56% predicts enrollment of 16 subjects (rounded up to 20) per indication. Since the five cleared indications and the proposed sample sizes are identical for the two clinical investigation arms, the sample size of one indication ( $n=20$ ) will be multiplied by five to reflect the total underlying subject population adequately. As a result, an enrollment target of 100 subjects in total will be aspired (ideally, but not necessarily, composed with 20 subjects per indication).

## 11.2. ANALYSIS POPULATIONS

It is expected during this clinical investigation only one population for ReUnion RFX System per arm will exist and all subjects will be analyzed “Per Protocol” (PP). However, it cannot be fully avoided that in theory subjects might need to be excluded from the PP population. In this occasion, there will be two groups being fully analyzed to ensure transparency and avoid bias.

The groups are defined as follows:

- **Intent-to Treat Population**

The Intent-to-Treat (ITT) Population is defined to be all enrolled subjects. An enrolled subject is a subject that has signed informed consent, all screening procedures have been successfully completed, is eligible and can receive treatment. The ITT population will not be analyzed for the annual reports and will only be included in the final report.

- **Per Protocol Population**

The PP Population is defined to be all subjects in the ITT Population with no major protocol violations. The protocol deviations that will exclude a subject are as follows:

- The subject does not receive the ReUnion RFX System

- The subject does not meet all eligibility criteria
- The subject has a protocol deviation that is considered likely to affect subject outcomes.

After the clinical investigation has been completed, a review of the data will be conducted to determine which subjects are to be excluded from the PP population.

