## 7. Clinical Investigation Design

This investigation is a prospective, multicenter clinical investigation. It is anticipated that a total of one hundred (100) subjects will be enrolled at approximately 5-10 sites. Neither subjects nor investigators are blinded to treatment and the clinical investigation does not include a contemporaneous control. The clinical investigation has been designed to follow the surgeon's standard of care for joint arthroplasty patients, which entails clinical evaluation on a regular ongoing basis, or as needed should the patient become symptomatic in the treated joint. The enrollment period is expected to occur over 20 months.

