## 9.2. EXCLUSION CRITERIA

- Subject has an active or suspected latent infection in or about the shoulder joint.
- Subject has mental or neuromuscular disorder which would create an unacceptable risk of prosthesis instability, prosthesis fixation failure or complications in postoperative care.
- Subject has bone stock compromised by disease, infection or prior implantation which cannot provide adequate support and/or fixation to the prosthesis.
- Subject has anticipated activities which would impose high stresses on the prosthesis and its fixation.
- Subject is obese such that he/she produces a load on the prosthesis which can lead to failure of fixation of the device or to failure of the device itself.
- Subject has severe concomitant disease(s) which may significantly affect the clinical outcome.
- For Total Shoulder Arthroplasty and Hemiarthroplasty: Subject has absent, irreparable or non-functioning rotator cuff and other essential muscles.

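### Per-protocol membership is decided after all outcomes are known, using eligibility criteria without thresholds, and neither document names the population that decides the primary conclusion

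*Protocol*

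**What the plan says.** **Population and timing of the decision.** Protocol 11.2 and SAP 5.1 expect one population, analysed per protocol. A subject leaves PP if the RFX System is not received, if any eligibility criterion is unmet, or if a deviation is judged likely to influence that subject's result. The decision comes at the end: "After the clinical investigation has been completed, a review of the data will be conducted to determine which subjects are to be excluded" from PP. If there are exclusions, PP and ITT are both to be analysed in full, with ITT in the final report only. ITT is all enrolled subjects, but enrolment is defined to include being eligible.

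**Design.** Protocol 7: "Neither subjects nor investigators are blinded to treatment and the clinical investigation does not include a contemporaneous control".

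**Criteria** (Protocol 9.2; letters as in the Synopsis). Each pairs a pre-operative condition with a risk:
- b: a mental or neuromuscular disorder creating an unacceptable risk of "prosthesis instability, prosthesis fixation failure or complications in postoperative care";
- c: compromised bone stock that "cannot provide adequate support and/or fixation to the prosthesis";
- d: anticipated activities that "would impose high stresses on the prosthesis and its fixation";
- e: obesity such that the subject "produces a load on the prosthesis which can lead to failure of fixation of the device" or of the device itself;
- f: concomitant disease that could significantly change the clinical outcome (qualified as severe in 9.2 but not in the Synopsis).

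None gives a cut-off, not even a BMI for e.

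**Recording of eligibility.** Inclusion and exclusion are recorded at the pre-operative visit (Protocol 10.4) and checked in monitoring (SAP 6.2, Table 6.2.1). That table leaves the individual answers and the count of eligible subjects out of both report types and substitutes a statement. Protocol 9.3 (v) foresees selection violations found after implantation.

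**Timing of the primary analysis.** Protocol 11.5.1 and SAP 4.2 place it in the annual report once all subjects have completed 24 months. SAP 6.6, Table 6.6.1, places it in the final report, and follow-up runs up to 10 years.

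**The concern.** Whoever carries out the closing review can see every ASES score, device-related event and reoperation. For a subject who did badly, criteria such as c or e leave room to argue that the bone stock or body weight was disqualifying all along. A subject with the same baseline and a good score offers less occasion for that argument.

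Each arm is tested as a single group against a fixed value (38.41 points in Arm A, 63.40 in Arm B). Removing low scores can therefore only raise the tested mean, and no control arm loses subjects under the same rule. At stake is whether a non-inferiority claim on PP keeps its stated 5% error, and whether an outside reader could tell if it did.

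**Working it through.** **1. The plan's own figure.** Standardised distance from the assumed mean to the limit:
- Arm A: (58.74 − 38.41)/20.33 = 1.00
- Arm B: (74.48 − 63.40)/11.08 = 1.00

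One-sample t-test, n = 10, two-sided 0.05, noncentrality 1.00 × √10 = 3.16: power 80.3%, as stated in both arms. The distances are equal and the t-test is scale-free, so the error rates below apply to either arm.

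**2. Inputs for the error check.**
- Test: one-sided at 5% (Protocol 11.3.2, SAP 3.1.1).
- True mean: exactly at the limit, where the error should be 5%.
- Scores: assumed normal.
- Evaluable n: not given per arm. At the stated 56% drop-out, 100 × 0.44 = 44 complete. All 44 in one arm is the upper extreme; an even split gives 22. I show 20 (close to an even split) and 44.
- Number removed, k: not in the documents. I show 0 to 2.

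**3. Procedure.** Draw n scores, remove k, compute t = (mean − limit)/(SD/√(n − k)), and reject if t exceeds the 95th percentile of t with n − k − 1 degrees of freedom (200,000 samples per setting). Removal is either random within the lower half of scores (mild) or of the k lowest scores (worst case).

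| n | k | random from lower half | k lowest |
|---|---|---|---|
| 20 | 0 | 5% | 5% |
| 20 | 1 | 7% | 13% |
| 20 | 2 | 9% | 24% |
| 44 | 0 | 5% | 5% |
| 44 | 1 | 6% | 11% |
| 44 | 2 | 8% | 18% |

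Removal unrelated to outcome (n = 22, 2 removed) leaves the error at 5.0%, so the inflation comes from linking removal to the score.

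**4. Which analysis the review can reach.**

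| Source | Primary analysis in | PP review done by then? | ITT available? |
|---|---|---|---|
| Protocol 11.5.1, SAP 4.2 | annual report after all 24-month visits | no | no |
| SAP 6.6, Table 6.6.1 | final report | yes, with all outcomes known | yes, if there are exclusions |

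On the final-report schedule the review feeds directly into the primary test. On the annual-report schedule it comes too late to do so, but PP membership is then not yet determined and ITT is not analysed. Neither schedule gives a primary population fixed in advance and without sight of outcomes.

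**The case against.** The strongest reply is that the criteria do not depend on outcome. A reader might infer from their wording that they are defined by what the implant later does. The documents do not support that: b needs a disorder, c needs bone stock already compromised by disease, infection or earlier implantation, and e needs obesity. Loosening alone establishes none of these, and no passage says that a post-operative event counts as evidence of ineligibility. Nor is the closing review confined to poor performers; the monitoring check is not either.

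A reader might also infer that failures will drop out of the primary test and out of view. That too goes beyond the text. Any PP exclusion triggers a full ITT analysis. Device-related events, reoperations and radiographic loosening have their own analyses (SAP 6.1, 6.5, 6.6, 6.7.3). The route to the primary test exists only on the final-report schedule. A subject whose implant is completely removed before 24 months may have no 24-month score at all, because continued annual ASES collection depends on at least partial implant survival (Protocol 11.3.2). PP exclusion would then change nothing for that subject.

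On size, removal of exactly the lowest scores is the extreme. If the device performs at the assumed benchmark mean, one-sided power is already 99.6% at n = 20, so removals would rarely change the conclusion.

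These points narrow the concern without closing it. Pre-operative records limit reclassification, but Protocol 9.3 (v) allows for later findings and the closing review is not tied to those records. ITT is a weak backstop: its definition requires eligibility, so a subject reclassified as ineligible could arguably leave ITT as well, and neither document says that ITT decides anything.

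**Conclusion.** The concern holds as a gap in the rule. The plan permits outcome-aware removal from the population it expects to analyse, and leaves the deciding population unnamed. It does not direct such removal, and nothing in the documents shows that it would run in one direction.

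With the true mean at the limit, one removal of a low scorer takes the one-sided error from 5% to about 7–13% at n = 20 or 6–11% at n = 44; two take it to 9–24% or 8–18%. The lower ends are random removal within the lower half of scores, the upper ends removal of the very lowest. These figures assume normal scores and the t-test, and they describe the PP analysis only. The number removed and the evaluable n are assumptions. They apply to the primary test if it is run after the closing review, as SAP Table 6.6.1 has it.

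The correction should be made before the 24-month primary analysis, because a list drawn up after the scores are known cannot credibly be shown to be independent of them.

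**What to change.** In Protocol 11.2 and SAP 5.1, replace the sentence that places the review after completion, so that:

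1. PP exclusion for eligibility rests only on facts recorded at or before surgery (the pre-operative inclusion/exclusion answers, baseline imaging, BMI). A post-operative event is not evidence that an exclusion criterion was met.
2. The list of PP exclusions, with reasons, is fixed and documented before the 24-month primary analysis is run, without reference to ASES, adverse event or reoperation data. This covers deviations judged likely to influence outcome as well as eligibility.
3. ITT is all enrolled subjects with no later eligibility re-check, is reported beside PP whenever the primary endpoint is analysed, and the deciding population is named in advance.
4. Protocol 11.5.1 and SAP 4.2 are reconciled with SAP 6.6, Table 6.6.1, on when the primary analysis takes place.

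The cost is wording in these sections and one documented review of data already collected. Because scores, events and reoperations appear in the annual reports, the review may need people kept apart from routine reporting, possibly extra staff. One downside remains: a truly ineligible subject discovered only through a later event stays in PP, which makes the result slightly less favourable.

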## 11.3. ANALYSIS AND EVALUATION

### 11.3.1. Statistical Analysis

Evaluation elements are defined as the questions on the CRF/eCRF. The SAP lists all evaluation elements and secondary elements which will be based on calculations between two or more evaluation elements.

All quantitative variables, including those based on calculations (secondary elements), will be analyzed with a case summary evaluation before the detailed characteristics and parameters can be evaluated. A case summary contains a listing of the number of valid cases/values, missing cases/values (if any) and total cases/values in the specific analysis. In general, as central position parameter for quantitative variables the mean, median and mode will be analyzed. As variation parameter the standard deviation, 95% confidence interval of the mean, interquartile range and range (based on maximum and minimum) will be calculated. All quantitative variables will be assessed for normality using the Shapiro-Wilk test. For optional visualization of quantitative variables, box-and-whisker plots will be used. Additional analyses like skewness and kurtosis measures or standard errors are optional also.

All qualitative variables, including those based on summaries (secondary elements), will be analyzed listing the proportions, frequencies, column and row totals, and missing proportion, if any.

The SAP reflects this approach and specifies the variables characteristics (quantitative or qualitative) in detail together with the related analysis strategy. This also includes calculation and summaries based on primary elements and the required analysis.

### 11.3.2. Primary Analysis / Endpoint

The objective of the clinical investigation is to demonstrate the non-inferiority (equal or better) of the ASES Shoulder Score in relationship to the officially cleared indications in comparison to respective clinical outcome data in the scientific literature.

Data collection of ASES Shoulder Score will be collected according to the schedule in Table 1, Schedule of Events. This will be repeated annually in all subjects who have the prosthesis with full or partial implant survival (including all subjects without removal of all endo-prosthesis components).

The 24 months postoperative results for subjects implanted with ReUnion RFX System will be compared to a historical group and results reported by respective clinical outcome data in the scientific literature.

[figure not shown]
Higher ASES Shoulder Score results are linked to better subject results and vice versa.

The clinical investigation endpoint is non-inferiority to the control, meaning the clinical investigation result should be equal or better than the control. In this clinical investigation, an equal or better ASES Shoulder Score result means equal or more ( $\geq$ ). As only results from samples will be captured, results are mostly estimates of the true population parameter. These

estimates vary by a certain area, where it is expected that the true population parameter falls within. Based on this, it is required to specify a lower limit for the acceptable difference or zone of indifference, denoted as  $-\theta$ .

Hypotheses are developed to allow for a comparison of the 24 months postoperative ASES Shoulder Score effectiveness/performance between the two underlying populations. The 24 months post-operative ASES Shoulder Score is the primary endpoint of this clinical investigation. Hypothesis tests will be one-sided with a significance level  $\alpha$  of 5%.

[figure not shown]
Table 3a: Arm A (TSA/HA)

Hypothesis	Equations	Interpretation
Null ( $H_0$ )	$A - B < -\theta$	Central tendency of A is inferior to the central tendency of B.
	ReUnion RFX System (TSA/HA) – Control (Benchmark) $< -\theta$	
Alternative ( $H_1$ )	$A - B \geq -\theta$	Central tendency of A is non-inferior to the central tendency of B.
	ReUnion RFX System (TSA/HA) – Control (Benchmark) $\geq -\theta$	
		
Possible Evidence (p)	Possible Decisions	Possible Conclusions – ASES score
p-value $> \alpha$ (0.05)	Fail to reject null hypothesis ( $H_0$ )	ReUnion RFX System (TSA/HA) $<$ Control (Benchmark) Insufficient evidence to reject the null hypothesis ( $H_0: A - B < -\theta$ ) at the pre-determined significance level of 5%.
p-value $\leq \alpha$ (0.05)	Reject null hypothesis ( $H_1$ )	ReUnion RFX System (TSA/HA) $\geq$ Control (Benchmark) Sufficient evidence to reject the null hypothesis ( $H_0: A - B < -\theta$ ) at the pre-determined significance level of 5%.

The primary objective of the clinical investigation is to demonstrate non-inferiority of the ASES Shoulder Score at 24 months post-operative compared to the benchmark literature for Arm A. The 24 months mean ASES Shoulder Score result of the RFX System (TSA/HA) will be compared to the pooled postoperative mean estimate of the control group (58.74 points). The pooled standard deviation of the post-operative ASES Shoulder Score result of the benchmark (20.33 points) was used to determine lower limit. The lower maximum acceptable difference ( $-\theta$ ) is 38.41 points (mean of control -  $\theta$  or  $58.74 - 20.33 = 38.41$  points).

Based on the underlying distribution of the data and the result of the normality assessment, either the parametric one-sample t-test or the non-parametric one-sample sign test will be used to compare the 24 months postoperative ASES Shoulder Score results of the ReUnion RFX System (RSA) against the value of 38.41 points.

Table 4a: Arm B (RSA)

Hypothesis	Equations	Interpretation
Null ( $H_0$ )	$A - B < -\theta$	Central tendency of A is inferior to the central tendency of B.
	ReUnion RFX System (RSA) – Control (Benchmark) $< -\theta$	
Alternative ( $H_1$ )	$A - B \geq -\theta$	Central tendency of A is non-inferior to the central tendency of B.
	ReUnion RFX System (RSA) – Control (Benchmark) $\geq -\theta$	
		
Possible Evidence (p)	Possible Decisions	Possible Conclusions – ASES score
p-value $> \alpha$ (0.05)	Fail to reject null hypothesis ( $H_0$ )	ReUnion RFX System (RSA) $<$ Control (Benchmark) Insufficient evidence to reject the null hypothesis ( $H_0: A - B < -\theta$ ) at the pre-determined significance level of 5%.
p-value $\leq \alpha$ (0.05)	Reject null hypothesis ( $H_1$ )	ReUnion RFX System (RSA) $\geq$ Control (Benchmark) Sufficient evidence to reject the null hypothesis ( $H_0: A - B < -\theta$ ) at the pre-determined significance level of 5%.

The primary objective of the clinical investigation is to demonstrate non-inferiority of the ASES score at 24 months post-operative compared to the benchmark literature for Arm B. The 24 months mean ASES Shoulder Score result of the RFX System (RSA) will be compared to the pooled postoperative mean estimate of the control group (74.48 points). The pooled standard deviation of the post-operative ASES Shoulder Score result of the benchmark (11.08 points) was used to determine the lower limit. The lower maximum acceptable difference ( $-\theta$ ) is 63.40 points (mean of control -  $\theta$  or  $74.48 - 11.08 = 63.40$  points).

Based on the underlying distribution of the data and the result of the normality assessment, either the parametric one-sample t-test or the non-parametric one-sample sign test will be used to compare the 24 months postoperative ASES Shoulder Score results of the ReUnion RFX System (RSA) against the value of 63.40 points.

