## 6. Introduction

Proximal humerus fractures currently represent one of the most difficult surgical procedures in the upper extremity. Besides conservative treatment and open reduction and internal fixation (ORIF) with plates or intramedullary nails, shoulder arthroplasty represents an alternative treatment option for certain indications. Industry currently provides modular options allowing for easy, streamlined intraoperative decision making between anatomical hemiarthroplasty (HA), anatomical total shoulder arthroplasty (TSA) and reverse shoulder arthroplasty (RSA) as well as the option for later conversion or revision utilizing a prior well-fixed humeral stem.

The ReUnion RFX System is indicated for use as a HA, TSA or RSA. It includes a humeral fracture stem component which can be used in conjunction with the ReUnion TSA or ReUnion RSA humeral and glenoid components.

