## 9.3. WITHDRAWAL CRITERIA

If during the clinical investigation a subject must be prematurely withdrawn, then the procedures outlined in this section must be followed. These procedures should not interfere with the initiation of any new treatments that are necessary to treat a subject's condition. Information on all withdrawn subjects will be documented.

Subjects may be withdrawn from the clinical investigation for any of the following reasons:

- Subject Withdrawal: A subject may voluntarily withdraw from the clinical investigation at any time and for any reason. The subject should be asked when possible, and without any form of coercion, the reason for his/her decision. If the participant withdraws from the clinical investigation completely, then data collected up until the point of withdrawal will be included in the final analysis.

- ii. Lost to Follow-Up (LTFU): A subject will be considered LTFU after all reasonable efforts have been made to contact the subject and request his/her continued participation in the clinical investigation. All attempts to contact the subject must be documented and should include at least two attempts to contact the subject by phone and one attempt via a certified letter. Data collected up until the point where the subject is LTFU will be included in the final analysis.
- iii. Removal of Device or AE/Incident: The discontinuation of a subject's participation in the clinical investigation due to the removal of the ReUnion RFX System or AE/incident that prohibits his/her continued participation must be fully explained. All available information concerning the removal of the device or AE/incident should be provided. Data collected up until the point of removal or AE/incident will be included in the final analysis.
- iv. Death: The discontinuation of a subject's participation in the clinical investigation due to death must be fully explained. All available information concerning the death or AE should be provided. Removal of a subject from continued follow-up in the clinical investigation due to death will not be considered a device failure unless the death is directly caused by, or attributable to, the ReUnion RFX System. Data collected up until the point of death will be included in the final analysis.

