2.1. BACKGROUND AND RATIONALE

The ReUnion RFX System is indicated for use as a hemiarthroplasty (HA), total shoulder arthroplasty (TSA) or reverse shoulder arthroplasty (RSA). It includes a RFX Stem that can utilize either the ReUnion TSA or ReUnion RSA humeral and glenoid components.

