3.1.1. Primary Analysis / Endpoint

The objective of the clinical investigation is to demonstrate the non-inferiority (equal or better) of the ASES Shoulder Score in relationship to the officially cleared indications in comparison to respective clinical outcome data in the scientific literature.

Data collection of ASES Shoulder Score will be collected according to the schedule in Table 1, Schedule of Events. This will be repeated annually in all subjects who have the prosthesis with

full or partial implant survival (including all subjects without removal of all endo-prosthesis components).

The 24 months postoperative results for subjects implanted with ReUnion RFX System will be compared to a historical group and results reported by respective clinical outcome data in the scientific literature.

Higher ASES Shoulder Score results are linked to better subject results and vice versa.

The clinical investigation endpoint is non-inferiority to the control, meaning the clinical investigation result should be equal or better than the control. In this clinical investigation, an equal or better ASES Shoulder Score result means equal or more (\geq). As only results from samples will be captured, results are mostly estimates of the true population parameter. These estimates vary by a certain area, where it is expected that the true population parameter falls within. Based on this, it is required to specify a lower limit for the acceptable difference or zone of indifference, denoted as $-\theta$.

Hypotheses are developed to allow for a comparison of the 24 months postoperative ASES Shoulder Score effectiveness/performance between the two underlying populations. The 24 months post-operative ASES Shoulder Score is the primary endpoint of this clinical investigation. Hypothesis tests will be one-sided with a significance level α of 5%.

Arm A (TSA/HA)		
Hypothesis	Equations	Interpretation
Null (H_0)	$A - B < -\theta$	Central tendency of A is inferior to the central tendency of B.
	ReUnion RFX System (TSA/HA) – Control (Benchmark) $< -\theta$	
Alternative (H_1)	$A - B \geq -\theta$	Central tendency of A is non-inferior to the central tendency of B.
	ReUnion RFX System (TSA/HA) – Control (Benchmark) $\geq -\theta$	
Possible Evidence (p)	Possible Decisions	Possible Conclusions – ASES score

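### Protocol 9.3 iii permits withdrawal when the RFX System is removed, while 11.3.2 and SAP 3.1.1 keep scoring partial implant survival, so a 24-month ASES after stem removal may be lost or tested with no stated rule

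*Protocol*

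**What the plan says.** **Withdrawal.** Protocol 9.3 opens its list with "Subjects may be withdrawn from the clinical investigation for any of the following reasons". Item iii then requires that a discontinuation "due to the removal of the ReUnion RFX System or AE/incident that prohibits his/her continued participation must be fully explained". It adds: "Data collected up until the point of removal or AE/incident will be included in the final analysis".

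**Continued scoring.** Protocol 11.3.2 has the ASES collected by the schedule of events and repeated annually in "all subjects who have the prosthesis with full or partial implant survival (including all subjects without removal of all endo-prosthesis components"). SAP 3.1.1 repeats the rule: "full or partial implant survival (including all subjects without removal of all endo-prosthesis components").

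**The device.** Protocol section 6 says of the RFX System: "It includes a humeral fracture stem component which can be used in conjunction with the ReUnion TSA or ReUnion RSA humeral and glenoid components". SAP 2.1 is similar: "It includes a RFX Stem that can utilize either the ReUnion TSA or ReUnion RSA humeral and glenoid components".

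**The primary test.** SAP 6.6 tests the total ASES at 24 months, by arm, against 38.41 (Arm A) or 63.40 (Arm B), with no condition on revision status. The device-related per-protocol exclusion in Protocol 11.2 is "The subject does not receive the ReUnion RFX System"; later removal is not mentioned. Missing values are counted and reported (Protocol 11.4, SAP 4.6), with no imputation or failure rule.

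**The concern.** Take a subject whose RFX stem is removed or exchanged before month 24 and who keeps, say, a glenoid component or baseplate. If this counts as removal of the RFX System, 9.3 iii allows withdrawal and the 24-month score is never obtained. If it counts as partial implant survival, scoring continues and the score is tested.

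The choice is open to each site, and the study is unblinded. A stem removal is the kind of outcome a device study should not lose from its efficacy result, and the loss would be selective rather than random. Where the subject is scored, the result may reflect a replacement stem, and the report would not say so. In both cases the content of the primary endpoint depends on a term that the plan does not define.

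**Working it through.** **1. Whether another passage settles it**

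| Place | What it covers | Decides the case? |
|---|---|---|
| Protocol 9.3 iii | Permits withdrawal on removal of the RFX System | No: removal is not defined for a stem alone |
| Protocol 11.3.2, SAP 3.1.1 | ASES continues unless all components are out | No: silent on withdrawal under 9.3 |
| Protocol 11.2, SAP 5.1 | Per-protocol exclusions | No: later removal is not named |
| Protocol 11.4, SAP 4.6 | Missing data counted | No |
| SAP 6.6 | Uses the 24-month score | No: no revision condition |
| Protocol 11.3.3, SAP 6.7.3 | Kaplan-Meier for reoperation | No: separate from the primary test |

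**2. Size of the shift in the mean**

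The plan gives no revision rate and no score after revision, so both are assumed. If a share r of the arm has the stem removed and scores D points lower, keeping these subjects instead of losing them lowers the mean by r × D.

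- r = 2%, D = 10: 0.02 × 10 = 0.2 points.
- r = 15%, D = 40: 0.15 × 40 = 6.0 points.

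The distance from benchmark mean to test value is 20.33 in Arm A and 11.08 in Arm B. The shift is therefore 1% to 30% of that distance in A (0.2/20.33 to 6.0/20.33) and 2% to 54% in B (0.2/11.08 to 6.0/11.08).

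**3. The plan's own power figure**

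Inputs are from Protocol 11.1.1 and 11.1.2. Effect size d = (mean − test value)/SD:

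- Arm A: (58.74 − 38.41)/20.33 = 1.00.
- Arm B: (74.48 − 63.40)/11.08 = 1.00.

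One-sample t-test power comes from the noncentral t distribution with n − 1 degrees of freedom and noncentrality d√n. At n = 10 and two-sided 5% it is 80.3%, which reproduces the plan. Protocol 11.3.2 sets the analysis at one-sided 5%; this gives 89.8% at n = 10, 86.2% at n = 9 and 99.8% at n = 22.

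**4. One such subject in an arm**

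Simulation with normal scores, plan means and SDs, one-sided 5% t-test, 100,000 to 200,000 runs per case, and one subject's score lowered by D. Repeat runs differ by up to about half a percentage point.

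| Evaluable | Handling of the one subject | Arm A | Arm B |
|---|---|---|---|
| 10 | No such subject | 90% | 90% |
| 9 | Dropped | 86% | 86% |
| 10 | Kept, 10 lower | 86% | 82% |
| 10 | Kept, 20 lower | 82% | 69% |
| 10 | Kept, 30 lower | 75% | 48% |
| 16 | Kept, 30 lower | 96% | 88% |
| 20 | Kept, 30 lower | 99% | 96% |
| 22 | Kept, 30 lower | 99% | 98% |

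**5. Which n applies**

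Ten is the plan's figure per indication, inflated to 16, rounded to 20 and multiplied by five to reach 100. The primary test is per arm, and the split between arms is not fixed. Assuming 50 per arm and 56% lost, 50 × 0.44 = 22 remain. For an arm to end with 10 evaluable at the same loss, it would have enrolled about 10/0.44 = 22.7, or 23 of the 100. The title of the study cited for the 56% gives a minimum follow-up of 10 years, so loss by month 24 could be smaller and the evaluable number larger.

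**The case against.** **Section 9.3 is permissive.** A reader might infer that it ends participation on removal. It says that subjects may be withdrawn, and the qualifier about prohibiting continued participation can be read as limiting removal as well as adverse events. This stands: no mandatory exit is written. It leaves the outcome to discretion, however, and so does not supply a rule.

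**The sections may agree.** If removal of the RFX System means the whole construct, 9.3 iii and 11.3.2 stop at the same point. The conflict needs a reading of the System as the stem, which the device descriptions suggest but do not define. In a hemiarthroplasty without a glenoid component, taking out stem and head removes everything, and the two sections agree. The gap is confined to the other cases.

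**The continued-scoring clause may not reach month 24.** It governs annual repetition, and the schedule of events has separate columns for 24 months and for annual visits. On that reading the schedule alone governs month 24. It carries no removal rule, so the question stays open.

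**A score after exchange need not belong to another device.** A reader might infer that it is credited to a device no longer implanted. The replacement could be another RFX stem, so this is possible but not general.

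**Failures are not hidden.** Reoperations are collected, coded by type and analysed by Kaplan-Meier, and missing scores are reported. This is correct and limits the harm, but none of it corrects the primary mean.

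**Conclusion.** The point holds as an undefined case in the primary analysis. For a stem taken out with other components left, the plan permits two treatments of the 24-month ASES and has no rule to choose between them. Withdrawal would selectively remove device failures and raise the arm mean, provided these subjects score below the rest. That assumption is plausible, but the plan gives no data on it.

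A reader might conclude that one such subject can decide an arm's result. The documents do not support that in general. The large power changes (to 75% in Arm A and about 48% in Arm B, for a 30-point deficit) need an arm with about 10 evaluable subjects. At about 22 evaluable the same subject leaves power at 99% and 98%, against 99.8% without. At a 10-point deficit the choice matters little even at n = 10. The reason to act is mainly the bias and the unclear meaning of the reported mean; power is a concern only if one arm turns out small.

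**What to change.** - Reconcile Protocol 9.3 iii with Protocol 11.3.2 and SAP 3.1.1, and define removal of the ReUnion RFX System, including the case of a stem taken out with other components left.
- State that removal or exchange of the stem does not by itself end study follow-up, and that the scheduled ASES, including month 24, is still collected unless the subject withdraws consent. This concerns observation only.
- Keep these subjects in the arm's primary analysis with their observed score.
- Add one pre-specified sensitivity analysis that counts RFX stem removal before month 24 as a failure. In the sign test this is any value below 38.41 (Arm A) or 63.40 (Arm B). In the t-test it must be a fixed low score stated in advance, since a value described only as below the limit cannot be used.
- Do not redefine implant survival by the stem for ASES collection. Under the wording of 11.3.2 that would stop the annual ASES in the very subjects who should be followed.

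**Cost.** Wording in two protocol sections and the SAP, a little more follow-up, and one extra analysis. The reoperation codes in SAP Table 6.1.2 may already identify these subjects: some come in pairs whose names suggest with and without humeral stem, which is an inference from the names. The arm result may be slightly less favourable.
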